	Prevalence of needs by follow demographic/clinical variable	$\operatorname{ss}(?)$		
Services rendered	reported needs	ays initiated in response to AYAs'	Providers	Fidelity Checklist
	needs reported by AYAs	esources rendered in response to	AYAs	Postintervention AYA survey
Care coordination	The delivery of multidisciplinary services to address needs reported by AYAs	AYA's receipt of services/ resources from across disciplines to address reported needs within one month of needs assessment completion	AYAs	Postintervention AYA survey
Needs met	Extent to which services and resources received met reported needs	AYAs' perception of the degree to which their needs were adequately addressed during the study period	AYAs	Postintervention AYA survey

Analytical Plan

Aim1. I will report descriptive

statistics on demographic and clinical variables. I will also calculate descriptive statistics on all quantitative implementation outcomes. Index scores will be generated for each measure by calculating an unweighted average of items within each construct. Further, I will conduct bivariate analyses to assess whether implementation outcomes vary by demographic and clinical variables to ensure that AYA NA-SB is feasible, acceptable, and appropriate across patient characteristics.

Qualitative interview data will be analyzed using template analysis²¹ based on a priori themes (i.e., Proctor's model and CFIR constructs) but allowing for additional emergent themes. A peer and I will independently abstract data from interview transcriptions per Proctor outcomes and CFIR constructs and discuss discrepancies until consensus is reached. When necessary, a third party will be pulled in to resolve discrepant coding.

Aim 2. I will calculate descriptive statistics on AYAs' identified needs, reporting the prevalence of specific needs and needs within specific domains, as well as on services received. I will also calculate descriptive statistics on quantitative service and patient outcomes. I will conduct bivariate analyses to assess whether service and patient outcomes vary by demographic and clinical variables.

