Appendix B: Fidelity checklist

Assessment ID					
(see top of assessment)					
Assessment Date (see timestamp at top of			/ /		
assessment)				-	
Date I reviewed assessment			//	_	
Date in which I initiated referral pathways			//	_	
Referral pathways initiated	Need # Referral Pathway				
For needs indicated by this	Completely	Disagree	Neither agree	Agraa	Completely
AYA, I was confident about	disagree	Disagree	nor disagree	Agree	agree
which referral pathways to initiate	0	2	3	4	S

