Appendix C: Postintervention AYA survey

Acceptability of Intervention Measure (AIM)

	Completely disagree	Disagree	Neither agree nor disagree	Agree	Completely agree
1. The needs assessment meets my approval.	①	2	3	4	(5)
2. The needs assessment is appealing to me.	①	2	3	4	(5)
3. I like the needs assessment.	①	2	3	4	(5)
4. I welcome the needs assessment.	①	2	3	4	(5)

Intervention Appropriateness Measure (IAM)

	Completely disagree	Disagree	Neither agree nor disagree	Agree	Completely agree
1. The needs assessment seems fitting.	①	2	3	4	(5)
2. The needs assessment seems suitable.	①	2	3	4	(5)
3. The needs assessment seems applicable.	①	2	3	4	(5)
4. The needs assessment seems like a good match.	①	2	3	4	(5)

Feasibility of Intervention Measure (FIM)

	Completely disagree	Disagree	Neither agree nor disagree	Agree	Completely agree
1. The needs assessment seems implementable.	①	2	3	4	(5)
2. The needs assessment seems possible.	①	2	3	4	(5)
3. The needs assessment seems doable.	①	2	3	4	(5)
4. The needs assessment seems easy to use.	①	2	3	4	(5)

Face validity/ content validity

	Completely disagree	Disagree	Neither agree nor disagree	Agree	Completely agree
1. The needs assessment helped me to communicate my needs.	1	2	3	4	(5)
2. The needs assessment was relevant to me.	①	2	3	4	(5)
3. The needs assessment included all needs that I was concerned about.	•	2	3	4	\$

Usability

e successive y					
	Completely disagree	Disagree	Neither agree nor disagree	Agree	Completely agree

1. I think that I would like to complete the needs assessment again.	①	2	3	(4)	(5)
2. I found the needs assessment too complicated.	①	2	3	4	(5)
3. I think the needs assessment was easy to complete.	①	2	3	4	(5)
4. I think I would need help to complete the needs assessment.	①	2	3	4	(5)
5. I felt very confident completing the needs assessment.	1	2	3	4	(5)

Usefulness

	Completely disagree	Disagree	Neither agree nor disagree	Agree	Completely agree
1. The needs assessment provided a helpful way for me to tell my doctors what I need.	①	2	3	4	(5)
2. I did use or would use services and resources offered to me by my doctors based on the needs I checked in the needs assessment.	•	2	3	4	⑤

Care coordination/Needs met

	Yes	No
1. I reported no needs on the needs assessment	① (skip to end)	©
2. I received follow-up care for the needs I reported (e.g., referrals, counseling, other services or resources)	0	② (skip to end)

3. Please indicate the type of follow-up care that you received. (check all that apply)

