(1) communication from my primary oncology team
(2) a phone call or visit from a social worker
(3) a phone call or visit from a nurse navigator
(4) A referral to a specialist (e.g., fertility counselor, nutritionist, physical therapist, etc.)
(5) educational materials
(6) other

	Completely disagree	Disagree	Neither agree nor disagree	Agree	Completely agree
4. The follow-up care I received addressed my needs.	①	2	3	4	(5)

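### The survey item behind care coordination merges all specialists into one tick worded as a referral, so it measures cross-discipline receipt only coarsely

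*Combined protocol and SAP*

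**What the plan says.** The Outcome Measure(s) table lists care coordination among the Aim 2 service and patient outcomes. The definition is "The delivery of multidisciplinary services to address needs reported by AYAs" and the measure is "AYA's receipt of services/ resources from across disciplines to address reported needs within one month of needs assessment completion". The only data source named for it is the postintervention AYA survey.

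The relevant items are in Appendix C, under Care coordination/Needs met:

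- Item 2 is a yes/no gate: "I received follow-up care for the needs I reported (e.g., referrals, counseling, other services or resources". Those who answer no skip to the end.
- Item 3 reads "Please indicate the type of follow-up care that you received. (check all that apply". It has six options. Option 1 is "communication from my primary oncology team". Options 2 and 3 are worded as a call or visit, from a social worker and a nurse navigator respectively. Option 4 is "A referral to a specialist (e.g., fertility counselor, nutritionist, physical therapist, etc". Option 5 is educational materials and option 6 is other.
- Item 4 asks for agreement that the care received addressed the AYA's needs.

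The fidelity checklist (Appendix B) has a field headed "Referral pathways initiated", filled in by need number and pathway. The Analytical Plan for Aim 2 promises descriptive statistics and bivariate comparisons. It gives no rule for turning the item 3 ticks into a care-coordination variable.

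**The concern.** The outcome is about receipt, and about receipt across disciplines. Option 4 is weak on both. It records the referral step, where options 2 and 3 record actual contact, and it puts fertility, nutrition, physical therapy and any other specialist under a single tick. Much of the intervention's variety of disciplines would lie in that option.

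The protocol treats referral and receipt as different things. In the outcome table, services rendered has one row for pathways initiated (providers, checklist) and another for what was delivered (AYAs, survey). Option 4 takes the patient-side measure back to the provider-side event.

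The study procedures make an unfulfilled referral a practical possibility. Under Referral pathway initiation, depending on the AYA's preference, the implementation leader either starts the pathways or hands over a list of recommended referrals. An AYA given only a list could reasonably tick option 4 with no appointment made.

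Care coordination is in the study title, and Aim 2 is meant to supply proof-of-concept. If the survey does not ask whether a specialist service was received, no later analysis can recover it.

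**Working it through.** The plan states no figure for this outcome, so there is nothing to reproduce. Two checks apply.

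**1. Definition against instrument.**

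| Element of the outcome | What the survey records |
|---|---|
| Receipt from oncology team, social work, nurse navigation | Yes, one option each |
| Receipt from a specialist | Referral only |
| Which specialist, or how many | Not asked |
| Resources | Educational materials, option 5 |

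The checklist, if linked by assessment ID, can show which specialist pathways were started. It cannot show whether the service was received.

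**2. How much can still be determined.** To gauge the loss, take a yes/no indicator of at least two disciplines. This threshold is an assumption used only as a probe; the protocol sets none. Count each of options 1 to 3 as one discipline. Options 1 to 4 give 2^4 = 16 tick patterns.

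- Without option 4 there are 2^3 = 8 patterns. Two or more ticks among three options: 3 + 1 = 4 yes. None or one tick: 1 + 3 = 4 no. All 8 are determined.
- With option 4 there are 8 more.
  - *If a referral is accepted as receipt*, option 4 counts as at least one discipline. The 7 patterns with any of options 1 to 3 are yes, and option 4 alone is undetermined. Total determined: 8 + 7 = 15 of 16.
  - *If a referral is not receipt*, option 4 counts as zero or more. The 4 patterns with two or more of options 1 to 3 are yes. The other 4 (option 4 alone, or with exactly one of options 1 to 3) are undetermined. Total determined: 8 + 4 = 12 of 16.
- The exact number of disciplines is known only where option 4 is not ticked: 8 of 16.

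With all six options (64 patterns, option 5 carrying no discipline and option 6 an unknown number), the indicator is determined in 52 of 64 if a referral counts and 40 of 64 if it does not. The exact number is known in 16 of 64. These are counts of possible patterns, not expected shares of patients.

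**3. Effect of one misclassified AYA.** Planned N is 25 to 50 (Sample Size). The step in a proportion is 1/N: 1/25 = 4 percentage points and 1/50 = 2 percentage points. With fewer survey respondents, or after leaving out AYAs with no needs, the step is larger. The protocol gives no expected response rate.

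**The case against.** The best defence is that the item does more than the criticism allows. It is multi-select, and three provider types are listed separately. An AYA who ticks two or more of them is classified whatever one decides about option 4. A reader might infer that the outcome cannot be computed from this survey; the documents do not support that, since the probe indicator is determined in 12 of 16 patterns even on the strict reading. This part of the objection stands.

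The measure also covers resources as well as services, so educational materials belong in the item. Item 2 openly names referrals as an example of follow-up care, so a broad definition may be deliberate. Even so, a broad definition does not yield confirmed specialist receipt, which is what the outcome row describes.

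A reader might also infer that the item ranks patients wrongly: three specialists seen give one tick, while one social-work call plus an unfulfilled referral gives two. That recording is possible, but a wrong ranking follows only if ticks are counted, and the protocol states no count, cut-off or ranking. Nor do the documents give a rate at which referrals lead to visits, so no share of option 4 ticks can be called false.

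Finally, this is a single-arm pilot focused mainly on implementation outcomes. Care coordination is one of several descriptive Aim 2 outcomes, and no sample size or stated decision rests on it. That limits the weight of the point, but the change is still worth making because it is cheap.

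**Conclusion.** The concern holds in a limited form. Item 3 measures cross-discipline receipt only coarsely. Specialist care is one merged tick recorded at referral, so an unfulfilled referral counts as care received and several specialists seen count as one. Linking the checklist would partly repair the merging, by showing which pathways were started, but would not show receipt. The absence of a derivation rule leaves the handling of option 4 open at analysis.

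When a referral is not taken as receipt, 4 of 16 patterns of options 1 to 4 leave a two-discipline indicator undetermined, and 8 of 16 leave the number of disciplines unknown. The first figure rests on the assumed threshold; the second does not. Each misclassified AYA moves a proportion by 2 to 4 percentage points at N = 50 to 25, provided the outcome is summarised as a proportion. The number of AYAs affected is unknown. This is a cheap improvement to a descriptive outcome and does not threaten the study's main aim.

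**What to change.** - **Split option 4** by the specialist types on the site's tailored referral map. For each type, ask two things separately: 'I was referred' and 'I had a call/visit or received the service'.
- **State the derivation.** Base the care-coordination description on the 'received' responses. Report the number of disciplines received, alongside the number of domains in which the AYA reported needs.
- **Set no fixed two-discipline cut-off.** Pathways are triggered by domain, so an AYA with needs in one domain who was fully served by one discipline would be scored as uncoordinated.
- **Report referred-but-not-received separately**, and keep educational materials as a resource, not a discipline.
- **Item 2 can stay as the gate.** Because it names referrals, AYAs who were only referred should still reach item 3. Its yes responses should not be reported as receipt.

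The cost is a slightly longer survey item, a minor amendment, and possibly a lower reported proportion, because unfulfilled referrals would no longer count.

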To facilitate a systematic and patient-centered approach to delivering services and resources to address the unmet needs of adolescents and young adults (AYAs) with cancer, we developed in preliminary studies the AYA Needs Assessment & Service Bridge (AYA NA-SB). AYA NA-SB includes (1) a holistic PROM assessing AYAs' physical, psychosocial and practical needs and (2) a collection of referral pathways for connecting AYAs to services and resources based on the needs they report (see **Appendix A**). To optimize AYA NA-SB's usability (i.e., ease of use) and usefulness (i.e., link to services), promote cancer programs' receptivity to AYA NA-SB implementation, and anticipate implementation strategies needed to facilitate AYA NA-SB's successful implementation and sustainment, we conducted usability testing, an ethnographic user and contextual analysis, and iterative prototyping workshops with a multidisciplinary design team.

Our development process culminated in an intervention with high usability and usefulness, characteristics we expect to promote AYA NA-SB's successful implementation and achievement of desired outcomes; however, AYA NA-SB's implementation and efficacy remain untested. Thus, through this study, we will evaluate AYA NA-SB's implementation and establish proof-of-concept. To avoid creating a tool that is only applicable to its high-resource testing environment, I will also plan for AYA NA-SB's potential scale-up across diverse health systems serving AYAs with cancer.

Objectives

Aim 1. Assess the implementation of AYA NA-SB. I will pilot AYA NA-SB in the North Carolina Cancer Hospital (NCCH), with a primary focus on implementation outcomes.

Aim 2. Establish proof-of-concept for AYA NA-SB. I will use pilot data to generate preliminary evidence on the extent to which AYA NA-SB addresses AYAs' reported needs.

Aim 3. Plan for AYA NA-SB's scalability and sustainability in diverse health systems. I will conduct annual 60-minute semi-structured qualitative interviews with AYA providers and program leaders from approximately 8 health systems to proactively address challenges and prepare for future AYA NA-SB scale-up and sustainability.

Methods and Measures

Design

- Aim 1/2: Single-arm feasibility pilot
- Aim 3: qualitative interviews

Setting

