Aim 1/2: I will pilot AYA NA-SB in the North Carolina Cancer Hospital (NCCH). NCCH is a public, National Cancer Institute-designated Comprehensive Cancer Center located in central North Carolina, in a relatively metropolitan area. At NCCH, around 450 individuals ages 15-30 are diagnosed each year. About one third of these patients are treated in pediatric oncology and the remainder in adult oncology. NCCH's AYA program was established in 2015 with funding from a local nonprofit organization, the BeLoud Sophie Foundation. This funding was initially allocated towards hiring one fulltime employee (a social worker/program director) to provide AYA-specific care at NCCH. Since 2015, the program has evolved, hiring new AYA-specific staff members (e.g., nurse practitioner, fertility counselor) and expanding program activities and reach.

Aim 3: I will conduct interviews with providers and program leaders from AYA programs around the country.

Subjects selection criteria

• Inclusion Criteria

Aim 1/2: AYAs with cancer ages 18 through 39 currently in treatment at NCCH Aim 3: AYA providers and program leaders from around the country

• Exclusion Criteria

No exclusion criteria

• Sample Size

- Aim 1/2
 - \circ N=25-50 AYAs
 - o N=25/arm has been proposed as the minimum threshold of sample size for aims related to instrumentation. ¹⁸ Given that this is a single-arm pilot study, we have determined that a sample size between 25 and 50 is appropriate.
- Aim 3
 - N=8 AYA providers/ program leaders. Interviewees will be purposefully sampled such that
 they represent a range of health systems. As such, a sample size of 8 is expected to yield
 adequate data to meet the objectives of Aim 3.

Interventions and Interactions

Intervention (Aims 1, 2)

The intervention, AYA NA-SB, includes three components: (1) a needs assessment, (2) a map of referral pathways, and (3) implementation guidance (**Appendix A**).

Needs assessment. The needs assessment portion of AYA NA-SB is a 57-item PROM which includes nine domains: (1) information, (2) cancer care team, (3) physical health, (4) emotional health, (5) sexual and reproductive health, (6) health behaviors and wellness, (7) work and education, (8) peer support and programming, and (9) finances and everyday needs.

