Referral pathways. Each domain of the needs assessment triggers a specific referral pathway. For example, needs reported in the 'sexual and reproductive health' domain trigger a referral to a fertility counselor or specialist while needs reported in the 'work and education' domain trigger a social worker visit. NCCH will tailor the map of referral pathways to their institution prior to the onset of data collection such that AYAs' needs are triaged to the appropriate parties at their institution.

Implementation guidance. Based on data collected during AYA NA-SB development, we compiled a list of potential implementation barriers and implementation strategies hypothesized to mitigate them. Participating NCCH providers will be given this information to inform their own deployment of strategies. To enhance the real-world applicability of findings, the implementation strategies will not be explicitly prescribed to NCCH, but the strategies they use will be carefully documented to contextualize findings.

Instruments & procedure (Aims 1,2)

Provider training. Six weeks prior to the onset of data collection, participating NCCH providers will participate in a 3-hour group training to familiarize them with the intervention and pilot protocol. In addition to the implementation leader, additional relevant providers identified by the implementation leader will participate in this training.

During the first hour of the training, I will provide an overview of AYA NA-SB and its development as well as a detailed summary of the pilot protocol. During the second hour of the training, we will collaboratively identify appropriate referral pathway providers for each needs assessment domain, explicitly outlining the

processes needed to initiate these referral pathways. During the third hour, we will brainstorm potential implementation strategies that might be deployed to facilitate AYA NA-SB implementation.

Needs assessment administration. The needs assessment portion of AYA NA-SB will be administered to AYAs through a secure online survey platform, RedCAP, and will take approximately 15 minutes to complete. The survey link will be delivered to AYAs through a patient portal message from the implementation leader. AYAs will receive a \$15 incentive for completing the needs assessment.

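### AYAs report follow-up and needs met only globally, so Aim 2 can show the share of reported needs with a referral initiated but not the share followed up or addressed

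*Combined protocol and SAP*

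**What the plan says.** Under Objectives, Aim 2 is to "generate preliminary evidence on the extent to which AYA NA-SB addresses AYAs' reported needs". The Interventions and Interactions section describes the needs assessment as a "57-item PROM which includes nine domains", and says of the referral map: "Each domain of the needs assessment triggers a specific referral pathway".

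Three sources feed the Aim 2 outcomes:

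- **Needs assessment (Appendix A).** Each need is recorded as its own item.
- **Fidelity checklist (Appendix B).** For each assessment, the implementation leader enters the Assessment ID, the dates of review and initiation, and the need numbers with the pathway chosen for each. The Outcome Measure(s) table names this as the provider source for services rendered.
- **Postintervention AYA survey (Appendix C, Care coordination/Needs met).** Item 1 screens out AYAs who reported no needs. Item 2 is one yes/no statement, "I received follow-up care for the needs I reported", and a No ends the survey. Item 3 is a check-all list of six kinds of care. Item 4 is one five-point agreement item, "The follow-up care I received addressed my needs".

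The Outcome Measure(s) table defines needs met as "AYAs' perception of the degree to which" their needs were adequately addressed, with the AYA survey as the only source. The Analytical Plan for Aim 2 is descriptive. It reports needs by item and by domain, services received, and the service and patient outcomes.

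**The concern.** Need is recorded by item and domain, and the intervention acts by domain, but the patient's account of what followed is collected once for everything. An AYA with needs in five domains who was helped in one has a single yes/no to give on receipt and a single blended rating to give on whether needs were addressed. The domain-level prevalence that the Analytical Plan will report has no matching domain-level result on the patient side.

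At stake is the step between a referral being made and the AYA receiving something useful. Proof-of-concept for a tool that links needs to services depends on that step, and refining the referral map would draw on it too. The skip after a No on item 2 adds a second difficulty. AYAs with needs and no follow-up have no item 4 value, so a needs-met summary among respondents leaves out the people the bridge did not reach.

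**Working it through.** **1. The plan's own figure.** Counting Appendix A by domain gives 8 + 6 + 5 + 15 + 5 + 7 + 2 + 3 + 6 = 57 items in nine domains, as stated.

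**2. Which shares can be computed.** Each share is (needs with the event) / (needs reported).

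| Quantity | Denominator | Numerator | Available? |
|---|---|---|---|
| Pathway initiated | Appendix A, per need | Appendix B, per need number | Yes, linked by Assessment ID |
| Follow-up received | Appendix A, per need | Appendix C item 2, per person | No |
| Need addressed | Appendix A, per need | Appendix C item 4, per person | No |

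Item 3 does not fill the gap. Its specialist option puts fertility counseling and nutrition in one box, although they sit in different domains of Appendix A.

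**3. What a Yes on item 2 says.** If an AYA with m reported needs answers Yes after follow-up on at least one, the share followed up lies between 1/m and 100%. The lower limit is 20% for m = 5, 10% for m = 10, 5% for m = 20 and 1.8% for m = 57. The documents give no expected m.

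**4. Dependence within a person.** Let p be the chance of follow-up in a domain and k the number of domains with a need (both assumed). If domains are independent, the share answering Yes is 1 − (1 − p)^k. If follow-up is all-or-none within a person, it is p.

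| p | k | All-or-none | Independent |
|---|---|---|---|
| 0.2 | 3 | 20% | 49% |
| 0.3 | 5 | 30% | 83% |
| 0.5 | 5 | 50% | 97% |

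One implementation leader handles each assessment as a whole, so positive dependence is plausible. The last column is then an upper bound.

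**5. Skip rule.** Suppose 80% of AYAs with follow-up agree on item 4 and 50% to 90% of AYAs with needs receive follow-up (both assumed). Counting those without follow-up as not addressed, the share among all AYAs with needs is 0.5 × 0.8 = 40% to 0.9 × 0.8 = 72%, against 80% among those who see the item.

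**6. Would domain-level data be usable at N = 25 to 50?** Take five need-domains per AYA, a true share of 50%, full response and a within-person correlation (ICC) of 0.1 to 0.5 (all assumed). The design effect is 1 + (5 − 1) × ICC = 1.4 to 3.0. The 95% half-width is 1.96 × √(0.25 × design effect / (5N)):

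- N = 25: 10 to 15 percentage points
- N = 50: 7 to 11 percentage points

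For a single domain in which 30% have a need (assumed), about 8 to 15 AYAs contribute. The half-width is 1.96 × √(0.25/8) = 35 points to 1.96 × √(0.25/15) = 25 points.

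**The case against.** **Follow-up is not measured by one item alone.** A reader of Appendix C might infer that the study holds no need-level data on response to needs. The documents do not support that. The checklist ties pathways to need numbers, services rendered has a provider source as well as a patient source, and item 3 adds type of care. This stands, and it limits the point to patient-reported receipt and resolution. The checklist cannot supply those. It records what the implementation leader did and, where the AYA prefers, that may be only handing over a list of recommended referrals.

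**Item 4 fits the stated outcome.** Needs met is defined as a perceived degree, the plan promises no share of needs met, and Aim 2 seeks only preliminary evidence in a pilot focused on implementation. This also stands: the item does not contradict the plan. It remains too coarse to set beside domain-level prevalence.

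**No stated bias follows.** A reader might infer that coverage of 20% to 50% would be reported as 49% to 97%. That needs independent domains and someone reading item 2 as coverage, and the plan does neither. Item 2 asks about the reported needs together, so an AYA helped with only some might also answer No.

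**A pilot this small cannot rank pathways.** Correct. Half-widths of 25 to 35 points allow description by domain and nothing more.

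**Conclusion.** The point holds in a limited form. As designed, Aim 2 can report the share of reported needs with a pathway initiated. It cannot report, overall or by domain, the share that AYAs say was followed up or addressed. The size of the gap is best given without a model: a Yes on item 2 is compatible with 1/m to 100% of m reported needs, assuming that the AYA answers Yes after any follow-up. The skip rule means that a needs-met percentage among item 4 respondents can stand well above the figure for all AYAs with needs (80% against 40% to 72% under the assumptions shown).

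This is an inexpensive improvement to measurement, not an error that undermines the pilot. Domain-level items would give an overall share with a half-width of roughly 7 to 15 points at the planned sample size, under the assumed numbers of needs and correlations and before nonresponse.

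**What to change.** - **Survey.** In REDCap, carry forward the domains in which the AYA reported a need (at most nine). For each, ask whether follow-up was received (yes/no) and whether the need was addressed (1 to 5). Keep items 2 to 4 as a summary. State which Appendix A responses count as a reported need, since the branching depends on it.
- **Linkage.** Join survey, needs assessment and checklist by Assessment ID. The planned bivariate analyses already require survey outcomes to be joined to demographics from the needs assessment. Say how AYAs who received only a list of recommended referrals are counted.
- **Analysis.** Report the proportion of need-domains with a pathway initiated, followed up and addressed, averaged per AYA, with an interval that allows for clustering within person. Count AYAs with needs but no follow-up in the denominator, for the global item 4 summary as well. Label by-domain results as descriptive.

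**Cost.** Branching logic and up to 18 short items. Appendix C has 26 numbered items planned at about 15 minutes, or 15 × 60 / 26 ≈ 35 seconds each. At that pace, needs in three to five domains add 6 to 10 items, about 3.5 to 6 minutes, and needs in all nine add about 10. Short repeated items may go faster. The added length falls on the AYAs with the most needs, so it should be checked in a short test before launch.
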